HBV	hepatitis B virus
HCV	hepatitis C virus
HIV	human immunodeficiency virus
IB	Investigator's Brochure
IC ₅₀	concentration that results in 50% inhibition

Abbreviations and Special Terms	Definition
IC ₉₀	concentration that results in 90% inhibition
ICF	informed consent form
ICH	International Conference on Harmonisation
IEC	independent ethics committee
[REDACTED]	[REDACTED]
IL	interleukin
IRB	institutional review board
IRT	interactive response technology
IV	intravenous
JAK	Janus kinase
MedDRA	Medical Dictionary for Regulatory Activities
PBMC	peripheral blood mononuclear cells
PD	pharmacodynamic
PGIC	Patient Global Impression of Change questionnaire
PI3K δ	phosphatidylinositol 3-kinase delta isoform
PJP	Pneumocystis jirovecii pneumonia
[REDACTED]	[REDACTED]
PROMIS	Patient-Reported-Outcomes Measurement Information System
QD	once daily
QTcF	QT interval corrected for heart rate using Fridericia's formula
RA	rheumatoid arthritis
RNA	ribonucleic acid
SGUS	salivary gland ultrasound
SLE	systemic lupus erythematosus
SoA	schedule of activities
SS	Sjögren's syndrome
T3, T4	triiodothyronine and thyroxine (thyroid hormones)
TB	tuberculosis
TEAE	treatment-emergent adverse event, AEs reported for the first time or worsening of a pre-existing event after first dose of study treatment
TNF	tissue necrosis factor
Treg	regulatory T cell
ULN	upper limit of normal

1. PROTOCOL SUMMARY

Protocol Title: An Open-Label Phase 2 Study of INCB050465 in Participants With Primary Sjögren's Syndrome

Protocol Number: INCB 50465-207

Objectives and Endpoints:

[Table 1](#) presents the primary and key secondary objectives and endpoints.

Table 1: Primary and Key Secondary Objectives and Endpoints

Objectives	Endpoints
Primary	
To determine the impact of INCB050465 on salivary gland echostructure	
Proportion of participants with a 1 point or greater improvement on the SGUS score for parotid and submandibular glands at Week 4 and Week 12
Key Secondary	
To assess the impact of INCB050465 on salivary CXCL13	
Change and percent change from baseline in salivary CXCL13 levels at Week 4 and Week 12
To evaluate the safety and tolerability of INCB050465	
Frequency, duration, and severity of AEs, clinical laboratory test results, vital sign results, ECGs, and physical examination findings

Overall Design:

[Table 2](#) presents the key study design elements. Further study details are presented after the table.

Table 2: Key Study Design Elements

Study Phase	Phase 2
Clinical Indication	Primary SS, moderate to severe in intensity
Population	Adults aged ≥ 18 years diagnosed with moderate to severe primary SS
Number of Participants	12
Study Design	This is a single group, open-label study of the impact of the PI3K δ inhibitor INCB050465 on signs and symptoms of SS. Twelve participants meeting the inclusion criteria and none of the exclusion criteria will be enrolled. Participants will receive treatment with INCB050465 1 mg QD for 12 weeks and undergo ultrasound measurement of salivary glands, measurements of salivary flow, collection of symptom questionnaires, and PD [REDACTED] blood sampling to allow studies of cytokine levels. [REDACTED] and other PD markers.

Table 2: Key Study Design Elements (Continued)

Estimated Duration of Study Participation	Screening: Up to 28 days Baseline: Day 1 Study drug administration: 12 weeks Follow up: 30 days (+ 7 days) after last dose of study drug Total: Up to 21 weeks
Data Monitoring Committee	No

Treatment Groups and Duration:

This is an open-label, Phase 2 study to assess the impact of PI3K δ inhibitor INCB050465 on signs and symptoms of SS. A single group of 12 participating adults, \geq 18 years old, who meet the inclusion criteria, will be enrolled for a duration of 12 weeks (with a 30-day safety follow-up period) and receive treatment with INCB050465 1.0 mg QD. Participants will undergo ultrasound measurement of salivary glands, measurements of salivary flow, collection of symptom questionnaires, and PD [REDACTED] blood sampling to allow studies of cytokine levels, gene expression levels, and other PD markers.

The study design is shown in [Figure 1](#).

Adherence to the study design requirements, including those specified in the SoA, is essential and required for study conduct.

[Table 3](#) provides the SoA for the study, and [Table 4](#) provides a Schedule of Laboratory Assessments.

Table 3: Schedule of Activities

	Screening (Day -28 to Day -1)	Day 1	Week 2 (± 3 Days)	Week 4 (± 7 Days)	Week 8 (± 7 Days)	Week 12/ EOT (± 7 Days)	Safety Follow-Up (30 Days [+7 Days] After Last Dose of Study Drug)	Comments
Administrative Procedures								
Informed consent	X							
Contact IRT	X	X	X	X	X	X		
Inclusion/exclusion criteria	X	X						
Medical and medication history	X							
Concomitant medications	X	X	X	X	X	X	X	
Dispense reminder card		X	X	X	X			
Administer study drug during visit		X	X	X	X			
Dispense study drug		X	X	X	X			
Drug accountability and compliance assessment			X	X	X	X		
Administer PJP prophylaxis if needed*		X	X	X	X	X	X	From Day 1 to at least 30 days after last dose of study drug. *See Section 6.6.1.1.
Safety Assessments								
AE assessment	X	X	X	X	X	X	X	
Comprehensive physical examination	X						X	
Targeted physical examination		X	X	X	X	X		Body systems with symptoms should be physically examined.
Vital signs	X	X	X	X	X	X	X	Measure height at screening only.
12-lead ECG	X	X	X			X	X*	*Standard ECG.
Efficacy Assessments								
Ultrasound of parotid and submandibular salivary glands		X*		X		X		*Schedule ultrasound 2 weeks before Day 1 to ensure results availability.
Measurement of total unstimulated salivary flow	X	X		X	X	X		
Measurement of total stimulated salivary flow	X*	X		X	X	X		*Documented measurement within 12 weeks before screening visit.
Questionnaire for dryness of eyes, mouth, and (females only) vagina	X	X		X	X	X		
ESSDAI assessment	X	X		X	X	X		
ESSPRI questionnaire	X	X		X	X	X		
PGIC questionnaire	X	X		X	X	X		
FSFI questionnaire	X	X		X	X	X		Female participants only.
PROMIS Fatigue questionnaire	X	X		X	X	X		
EQ-5D questionnaire	X	X		X	X	X		

Table 4: Schedule of Laboratory Assessments

	Screening (Day -28 to Day -1)	Day 1	Week 2 (± 3 days)	Week 4 (± 7 Days)	Week 8 (± 7 Days)	Week 12/EOT (± 7 Days)	Safety Follow-Up (30 Days [+ 7 Days] After Last Dose of Study Drug)	Comments
Clinical Laboratory Assessments								
Serum chemistries	X	X	X	X	X	X	X	
Hematology	X	X	X	X	X	X	X	
Serum pregnancy test	X						X	All female participants of childbearing potential.
FSH	X							To document hormonal menopause defined as amenorrhea of at least 12 months before screening
Urine pregnancy test		X	X	X	X	X		Female participants of childbearing potential only.
Thyroid function	X							
Serology – HIV, HBV, and HCV, viral load reflex if required	X							
TB test	X							QuantiFERON-TB Gold test or T-spot.TB.
Urinalysis	X					X	X	

2. INTRODUCTION

INCB050465 is an inhibitor of the Class IA PI3K enzymes, with selectivity for the delta isoform (PI3K δ), and is in development for treatment of hematologic malignancies, solid tumors, and autoimmune diseases. Uncontrolled B-cell and T-cell proliferation and differentiation are strongly implicated in the pathogenesis of hematologic malignancies and autoimmune diseases. PI3K δ serves a critical signal for B-cell and T-cell development. Overactive PI3K δ signaling leads to uncontrolled B-cell and T-cell proliferation and differentiation, which are strongly implicated in the pathogenesis of autoimmunity. [REDACTED]

2.1. Background

2.1.1. Sjögren's Syndrome

Sjögren's syndrome is a chronic autoimmune exocrinopathy, an inflammatory disease affecting the glands that produce tears, saliva, and vaginal and bronchial secretions. Thus, persistent dryness of the mouth and eyes caused by functional and structural impairment of the salivary and lachrymal glands are the hallmarks of the disease. Sjögren's syndrome is primarily a disorder of women in their sixth and seventh decade, although men and younger women can be affected. Sjögren's syndrome is found worldwide, with reported clinical characteristics similar in China, Japan, and California (Kang et al 1993).

Estimates of the incidence and prevalence of SS are difficult given the variety of criteria used in the various studies, with a range of 0.01% to 0.09% (Risselada et al 2014, Theander et al 2011, Vitali 2003). It would appear that only about 10% of all people with documented dry eyes have SS. In a population-based study from Olmsted County, MN, using the 1993 European SS criteria, the annual incidence of SS was approximately 4 per 100,000 people (Pillemer et al 2001). Of incident cases, 70% had primary SS. A 2014 meta-analysis of population-based studies found the incidence of SS to be approximately 7 per 100,000 people (Qin et al 2015), with the highest incidence rates in studies from Europe and Asia. The prevalence in the meta-analysis was estimated at 43 per 100,000 (0.043%).

The major clinical manifestations are dryness of the eyes and mouth caused by decreased lacrimal and salivary gland function (eg, decreased lacrimal and salivary gland function), causing dryness of the eyes and mouth (Pertovaara et al 1999, Ramos-Casals et al 2005). Isolated keratoconjunctivitis sicca is the form of ocular dryness that led Henrik Sjögren, in 1933, to initially describe clinical and histologic findings of the syndrome named after him.

Keratoconjunctivitis sicca represents a deficiency in production of the aqueous phase of the tear layer due to damage of the lacrimal glands; the term "dry eye syndrome" refers to the broad spectrum of disorders leading to ocular dryness.

In addition to the glandular/exocrine features noted above (which can also include significant swelling of the parotid salivary glands), there can also be significant extraglandular features affecting multiple organ systems, including inflammatory joint disease, interstitial pneumonitis, hematologic abnormalities and lymphoproliferative changes (non-Hodgkin lymphoma).

Sjögren's syndrome also affects nonexocrine organs ([Carsons and Bhimji 2017](#)). Sjögren's syndrome can be a primary process (unassociated with an underlying inflammatory process) or secondary, most often associated with RA (25%-35% of patients with RA have SS) or SLE. Other diseases or treatments can cause many or most of the clinical manifestations of SS (eg, prior head and/or neck irradiation, infection with HCV or HIV, lymphoma, sarcoidosis, graft-versus-host disease, and recent use of medications with anticholinergic properties). Serological abnormalities include the presence of autoantibodies (antinuclear antibodies, RF, and antibodies to Ro/SS-A and La/SS-B), hypocomplementemia, and cryoglobulinemia; vasculitis can also occur.

2.1.2. Diagnosis of Sjögren's Syndrome

The diagnosis of SS is a challenge as it shares multiple clinical and immunologic features with other autoimmune connective tissue disorders. Hence, there is no single diagnostic test for SS; the diagnosis is made based on appropriate clinical findings and laboratory results, after excluding other potential causes of ocular and/or oral dryness. The diagnosis should be considered in any individual with persistent dry eyes and/or mouth, especially if parotid gland enlargement or increase in dental caries are present. The diagnosis of SS can be made in individuals with an objective finding of ocular and/or oral dryness for whom there is substantive evidence of an underlying autoimmune basis targeting the exocrine glands and thereby causing dysfunction. A variety of classification criteria have been developed, but these are not appropriate for use as diagnostic criteria.

The variety of criteria and clinical, serologic, and histologic markers makes study of SS difficult and comparison of outcomes challenging. For the purposes of studies, the assured diagnosis is most often based on 2002 AECG criteria, which include the concurrent presence of various signs and symptoms represented in the 6 diagnostic standards ([Vitali et al 2002](#)):

1. Oral symptoms
2. Ocular symptoms
3. Evidence of oral signs
4. Evidence of ocular dryness

5. Evidence of exocrine gland dysfunction

6. Positive gland biopsy

A biopsy of a minor salivary gland on the inner aspect of the mouth remains an important diagnostic test, the degree of abnormality predicting the risk of developing lymphoma; additionally, extant primary lymphoma can be detected ([Foulks et al 2015, Saraux et al 2016](#)). A positive lip biopsy (showing focal lymphocytic sialadenitis with a focus score ≥ 1) is found in 66% to 89% of patients with SS classified by the 2002 AECG criteria, with a sensitivity of about 80%.

(magnetic resonance imaging and ultrasound identify inhomogeneity within the glandular parenchyma; scintigraphy and contrast sialography are less commonly used). Between 2013 and 2015, 5 studies of imaging techniques found that ultrasonography had a sensitivity of 55% to 66% and specificity of 93% to 98% for a diagnosis of SS ([Brito-Zeron and Ramos-Casals 2014](#), [Fazaa et al 2014](#), [Ramos-Casals et al 2010](#), [Ramos-Casals et al 2012](#), [Thanou-Stavraki and James 2008](#)).

2.2. Current Treatment and Unmet Needs for Sjögren's Syndrome

There is no disease-modifying treatment available for SS. The goals of current forms of therapy are to decrease symptoms of dryness in the eyes, mouth, and other affected areas (eg, vagina), prevent complications of mucosal dryness (eg, dental decay, corneal ulceration), detect and manage systemic manifestations of SS, and prevent progression of glandular disease to a lymphoproliferative state; these therapies do not address the underlying disease.

Current approaches have been summarized ([Foulks et al 2015](#), [Vivino et al 2016](#)) as follows. Initial therapy for all patients should be nonpharmacologic and preventive, which should include expert ophthalmologic and dental care, education, and assurance that all vaccinations are up-to-date. Secretagogues may be useful in patients for whom artificial tears and saliva do not suffice. Especially in secondary SS, interventions may be needed to address extraglandular manifestations (eg, skin, joint, blood vessel, pulmonary, and renal damage). These treatments are usually similar to those used for the underlying disorders (eg, SLE or RA) and can include nonsteroidal anti-inflammatory drugs, glucocorticosteroids, antimalarials (hydroxychloroquine), and nonbiologic disease-modifying antirheumatic drugs (eg, methotrexate, leflunomide, azathioprine, sulfasalazine, mycophenolic acid, and cyclosporine). For lymphoproliferative disease and the more severe extraglandular features of SS (eg, cryoglobulinemic vasculitis, interstitial lung disease, pulmonary hypertension, interstitial nephritis, glomerulonephritis, primary biliary cirrhosis, mononeuritis multiplex), other, more potent agents may be required (eg, cyclophosphamide or rituximab).

2.3. PI3K δ in Autoimmune Diseases

PI3Ks belong to a family of lipid signaling kinases that phosphorylate phosphoinositides of the inositol ring ([Cantley 2002](#)). PI3K enzymes are divided into 3 classes (Class I, II, and III) according to their structure, regulation, and substrate specificity. Class I PI3Ks, which include PI3K α , PI3K β , PI3K γ , and PI3K δ , are dual-specificity lipid and protein kinases that catalyze the phosphorylation of phosphatidylinositol 4,5-bisphosphate, giving rise to phosphatidylinositol (3,4,5)-trisphosphate, which functions as a second messenger that controls a number of cellular processes, including growth, survival, adhesion, and migration.

The delta isoform of PI3K is expressed primarily in hematopoietic cells and plays an essential role in B-cell development and function. Aberrant PI3K δ signaling activates and proliferates self-reactive B cells that produce autoantibodies, act as antigen-presenting cells presenting self-antigen to autoreactive T cells, and produce proinflammatory cytokines, and therefore has been strongly linked to autoimmunity ([Puri and Gold 2012](#)). 

The ability of PI3K δ inhibitors to reduce the severity of these inflammatory diseases may be due not only to their actions on B cells, but also to inhibitory effects on other immune cells that contribute to autoimmune disease such as T cells, mast cells and neutrophils (Fung-Leung 2011). Given the fact that in addition to B cells, autoreactive CD4+ T cells are involved in SS pathogenesis (Kasperkiewicz et al 2017), inhibition of PI3K δ signaling could have benefit in the treatment of patients with current unmet need in SS and other autoimmune diseases.

2.3.1. PI3K δ in Sjögren's Syndrome

Germinal center-like ectopic lymphoid structures are thought to play an important role in local chronic B-cell activation and clonal expansion, autoantibody production, and Ig class switching in SS (Bombardieri et al 2017, Salomonsson et al 2003). Importantly, a strong association between SS and polymorphisms in the CXCR5 locus has been reported (Lessard et al 2013). CXCR5 is the receptor for CXCL13 and is critical for the migration of B cells and T follicular helper cells into secondary lymphoid tissues. T follicular helper cells have been detected in the salivary glands of patients with primary SS within germinal center-like structures (Maehara et al 2012, Szabo et al 2014,) and are more frequent in the peripheral blood of SS patients compared with healthy controls (Jin et al 2014).

Genetic deletion or pharmacologic inhibition of PI3K δ leads to defective B-cell activation, reduced proliferation, and functional suppression (Bilancio et al 2006, Henley et al 2008, Vigorito et al 2004). The formation of T follicular helper cells and the production of key effector molecules is critically dependent on PI3K δ activity (Rolf et al 2010). Finally, CXCR5 receptor downstream signaling is partially PI3K δ -dependent, resulting in diminished chemotaxis and disrupted germinal center organization (Reif et al 2004).

[REDACTED]

2.4. Study Rationale

2.4.1. Scientific Rationale for Study Design

Currently, there is no approved therapy for SS that acts to improve all symptoms of this disease. Treatment is palliative and symptom-specific, and therefore there remains a significant unmet medical need for new treatments for SS.

[REDACTED]

2.4.2. Nonclinical Toxicology and Safety Margins

A series of nonclinical toxicity studies were completed to support human clinical studies with INCB050465. The toxicologic and toxicokinetic profiles of INCB050465 were characterized in single and repeat oral dose studies of up to 3 months in duration in rats and dogs. The most prominent findings observed included lymphoid depletion, most notably B-cell regions of multiple lymphoid organs, including lymph nodes, spleen, thymus, and GALT, at all doses.

[REDACTED] Reversibility of the effects on lymphoid system was clearly demonstrated.

[REDACTED]

[REDACTED]

Refer to the INCB050465 [IB](#) for additional details regarding the safety margins.

2.4.3. Justification for Dose

[REDACTED]

[REDACTED]

[REDACTED]

[figure not shown]
Refer to the INCB050465 [IB](#) for further details.

[REDACTED]

The most prominent findings following repeat-dose exposure to INCB050465 in both rats and dogs were lymphoid depletion, most notably B-cell regions, of multiple lymphoid organs, including lymph nodes, spleen, thymus, and gut-associated lymphoid tissue, at all doses. Lymphoid depletion was considered a DLT. Effects on the lymphoid system are an expected result of immunomodulatory effects of PI3K δ inhibition (Marone et al 2008, Pillai and Cariappa 2009). Reversibility of the effects on the lymphoid system was clearly demonstrated and would be expected to occur in a clinical setting.

INCB050465 was evaluated in 1-month (28 days) and 3-month (91 days) toxicology studies in Sprague Dawley rats and beagle dogs. In the rat studies, INCB050465 was administered daily for 1 month at doses of 10, 30, or 100 mg/kg per day or daily for 3 months at doses of 3, 7.5, or 15 mg/kg per day. In the dog studies, INCB050465 was administered daily for 1 month at doses of 1, 3, or 15 mg/kg per day or daily for 3 months at doses of 0.3, 0.75, or 1.5 mg/kg per day. Recovery was evaluated after a 4-week (1-month study) or 6-week (3-month study) recovery period in both species.

The primary effect observed in 1-month and 3-month studies in both rats and dogs was dose-dependent immunosuppression (evident as minimal to marked depletion of lymphoid tissues, including thymus, lymph nodes, spleen, and gut-associated lymphoid tissue), which was attributed to the pharmacologic activity of INCB050465. All lymphoid effects showed evidence of reversibility at the end of the study recovery periods.

[REDACTED]

[REDACTED]

[REDACTED]

[REDACTED]

The potential risk associated with INCB050465 clinical administration is expected to be low based on the proposed dose of 1 mg, adequate exposure margins, the demonstrated lack of findings in recovery animals following drug withdrawal, and comprehensive evaluation of safety and PK.

For more detailed information about the known and expected risks and reasonably expected AEs of INCB050465, refer to the [IB](#).

[REDACTED]

2.5.3. Potential Benefits of INCB050465 in Sjögren's Syndrome

Participants may experience clinically meaningful improvements in their SS signs and symptoms during the study and may additionally benefit from the comprehensive safety assessments conducted as part of the study (eg, clinical laboratory tests, physical examinations, ECGs).

Participants will also contribute to the process of developing a novel anti-inflammatory agent for SS, a condition with high unmet need that is severely debilitating to participants' well-being and daily functioning.

2.5.4. Overall Risk/Benefit Statement

[REDACTED]

3. OBJECTIVES AND ENDPOINTS

Table 5 presents the objectives and endpoints.

Table 5: Objectives and Endpoints

Objectives	Endpoints
Primary	
To determine the impact of INCB050465 on salivary gland echostructure.	
• Proportion of participants with a 1 point or greater improvement on the SGUS score for parotid and submandibular glands at Week 4 and Week 12.
Secondary	
To assess the impact of INCB050465 on salivary CXCL13	
• Change and percent change from baseline in salivary CXCL13 levels at Week 4 and Week 12.
To assess the efficacy of INCB050465	
• Change and percent change in stimulated and unstimulated whole salivary flow from baseline at Weeks 4, 8, and 12.• Change and percent change in ESSDAI at Week 12.• Change and percent change in ESSPRI at Weeks 4, 8, and 12.• Change and percent change in symptom scores for dryness of eyes, mouth, and vagina at Weeks 4, 8, and 12.• Proportions of participants in each PGIC category at Weeks 4, 8, and 12.• Change and percent change in PROMIS Fatigue short form at Weeks 4, 8, and 12.• Change and percent change in FSFI at Weeks 4, 8, and 12 (female participants only).• Change and percent change in EQ-5D at Weeks 4, 8, and 12.
To evaluate the safety and tolerability of INCB050465	
• Frequency, duration, and severity of AEs, clinical laboratory test results, vital sign results, ECGs, and physical examination findings.

Table 5: Objectives and Endpoints (Continued)

the *Journal of the American Statistical Association* (1980, 75, 311-322) and the *Journal of the Royal Statistical Society, Series B* (1981, 43, 1-37). The latter paper is the most comprehensive treatment of the topic.

4. STUDY DESIGN

4.1. Overall Design

This is a single group, open-label study of the impact of PI3K δ inhibitor INCB050465 on signs and symptoms of SS. Twelve participants meeting the inclusion criteria and none of the exclusion criteria will be enrolled. Participants will receive treatment with INCB050465 [REDACTED] QD for 12 weeks and undergo ultrasound measurement of salivary glands, measurements of salivary flow, collection of symptom questionnaires, and PD [REDACTED] blood sampling to allow studies of cytokine levels, gene expression levels, and other PD markers.

Participants will have regularly scheduled study visits at screening, Day 1 (baseline; first day of dose administration), and at the end of Weeks 4, 8 and 12, where laboratory and other assessments will be performed. There will also be a laboratory-only visit at the end of Week 2 to collect safety laboratory assessments [REDACTED]. Participants will complete questionnaires regarding signs and symptoms of disease at each study visit.

Ultrasound measurement of the parotid and submandibular glands will be performed on Day 1 (before the first dose) and after 4 and 12 weeks of treatment. Ultrasound of glands will be performed in the longitudinal and transverse planes with participants in a supine position. The ultrasound images will be evaluated for quality then transmitted to a central vendor for reading and data summarization.

The echostructure of each gland on B-mode images will be graded on a 5-point scale (0 to 4):

- Grade 0: normal homogeneous gland.
- Grade 1: small hypoechoic areas with hyperechoic bands.
- Grade 2: multiple hypoechoic areas less than 2 mm.
- Grade 3: multiple hypoechoic areas 2 to 6 mm.
- Grade 4: multiple hypoechoic areas larger than 6 mm.

For each timepoint, 4 grades will be obtained, one for each parotid and submandibular gland. The SGUS score is the numeric sum of the 4 individual grades (maximum score of 16). Instructions for conducting and transmitting ultrasound measurements will be provided in the Study Manual.

Stimulated and unstimulated salivary flow will be performed at baseline and after 4, 8, and 12 weeks of treatment. Instructions for performing salivary flow measurements will be provided in the Study Manual.

PJP prophylaxis: Prior treatment with prednisone or equivalent may represent a risk factor for PJP in combination with other immunosuppressants. Participants who have received prednisone \geq 20 mg per day (or equivalent) within 60 days before baseline are excluded. Participants receiving \geq 10 mg to $<$ 20 mg of prednisone (or equivalent) may be at increased risk for PJP, and prophylaxis should be considered for these participants, particularly if they have a history of PJP or have recently received any immunosuppressive therapy that may represent an increased risk. Participants receiving $<$ 10 mg of prednisone or equivalent have some potential risk. PJP prophylaxis is not required for these participants but should be considered by the investigator only in exceptional circumstances in consultation with the medical monitor as needed.

Examples of standard PJP prophylaxis therapies include trimethoprim-sulfamethoxazole, atovaquone, dapsone with or without pyrimethamine, and pentamidine ([Baden et al 2012](#)). Due to reports of cross-sensitivity between sulfonamides and dapsone, all participants who have a known or suspected allergy to sulfonamides must receive either inhaled pentamidine or atovaquone for PJP prophylaxis. Prophylaxis should be given while participants are receiving study drug and should continue for at least 30 days after the last dose of study drug.

In addition to these study visits, there will be laboratory-only visits at the end of Week 2 to collect safety laboratory assessments [REDACTED].

Week 12 will correspond to the EOT. A safety follow up visit will occur 30 (+7) days after the last dose of study drug.

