5.1. Inclusion Criteria

Participants are eligible to be included in the study only if all of the following criteria apply:

1. Ability to comprehend and willingness to sign a written ICF for the study.
2. Age \geq 18 years at the time of signing the ICF.
3. Primary SS diagnosed according to the revised AECG criteria ([Vitali et al 2002](#)), defined as presence of any 4 of the 6 items below, with at least items d) and f), or the presence of any 3 of items c), d), e) and f):
 - a. Ocular dryness symptoms.
 - b. Oral dryness symptoms.
 - c. Schirmer's test \leq 5 mm/5 min.
 - d. Focus score \geq 1 focus/4 mm² on minor salivary gland biopsy.
 - e. Unstimulated whole salivary flow \leq 0.1 mL/min.
[REDACTED]
4. Minimum score of 2 on the SGUS score for parotid and submandibular glands.
5. ESSDAI score \geq 5.
[REDACTED]
7. Symptomatic oral dryness score of at least 5 on patient questionnaire.
8. Willingness to avoid pregnancy or fathering children based on the criteria below:
 - a. Woman of nonchildbearing potential (ie, surgically sterile with a hysterectomy and/or bilateral oophorectomy OR \geq 12 months of amenorrhea and at least 50 years of age, and FSH levels $>$ 30 IU/L).
 - b. Woman of childbearing potential who has a negative serum pregnancy test at screening and negative urine pregnancy test before the first dose on Day 1 and who agrees to take appropriate precautions to avoid pregnancy (with at least 99% certainty) from screening through safety follow-up visit. Permitted methods that are at least 99% effective in preventing pregnancy (see [Appendix A](#)) should be communicated to the participant and her understanding confirmed.
 - c. Man who agrees to take appropriate precautions to avoid fathering children (with at least 99% certainty) or from sperm donation from screening through 93 days after treatment with INCB050465. Permitted methods that are at least 99% effective in preventing pregnancy (see [Appendix A](#)) should be communicated to the participant and his understanding confirmed.

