6.3. Measures to Minimize Bias: Randomization and Blinding

Not applicable.

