10. STATISTICS

10.1. Sample Size Determination

The sample size is based on the demonstration of preliminary findings of efficacy, which also depends on the occurrence of safety findings. Approximately 12 participants will be enrolled, which will provide > 90% chance of detecting at least 1 AE of interest (eg, platelets, hemoglobin, ANC, liver functions, and infections) if the underlying AE rate is 20%.

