4.1.3. Baseline Value

Baseline is the last nonmissing measurement obtained before the first administration of INCB050465.

When scheduled assessments and unscheduled assessments occur on the same day and time of the assessment or time of first dose is not available, use the following convention to determine baseline:

- If both a scheduled and an unscheduled visit are available on the day of the first dose and the time is missing, use the scheduled assessment as baseline.
- If all scheduled assessments are missing on the day of the first dose and an unscheduled assessment is available, use the unscheduled assessment as baseline.

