7.1. Efficacy Parameters

7.1.1. Ultrasound of Salivary Glands

The echostructure of each gland on B-mode images will be graded on a 5-point scales (0 to 4) as described by Gazeau et al (2018). Grade 0 indicates a normal homogeneous gland, Grade 1 small hypoechoic areas with hyperechoic bands, Grade 2 multiple hypoechoic areas < 2 mm, Grade 3 multiple hypoechoic areas 2 to 6 mm, and Grade 4 multiple hypoechoic areas > 6 mm. For each participant at each timepoint, 4 grades will be obtained, one for each parotid and submandibular gland. The SGUS score is the numeric sum of the 4 individual grades.

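### The plan states no masking of visit order for the central SGUS reads, and the qualifying pre-dose read appears to be the primary baseline, so a 1-point responder rule is open to reader expectation

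*Protocol*

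**What the plan says.** - **Design.** Protocol Section 4.1: "This is a single group, open-label study of the impact of PI3K δ inhibitor INCB050465 on signs and symptoms of SS". Section 10.1: "Approximately 12 participants will be enrolled". Every post-baseline scan is therefore an on-treatment scan.
- **Score and responder rule.** SAP Section 7.1.1: "The SGUS score is the numeric sum of the 4 individual grades". Each gland is graded 0 to 4, so the sum runs from 0 to 16. The primary endpoint (Protocol Section 3, SAP Section 2.2) is the proportion improving by 1 point or more, at Week 4 and at Week 12.
- **Reading.** Protocol Section 4.1: "The ultrasound images will be evaluated for quality then transmitted to a central vendor for reading and data summarization". Section 8.2.1 repeats this. Neither section gives the number of readers, the read order or any masking. The Study Manual is cited for performing and sending the scans, not for grading them.
- **Bias control.** Protocol Section 6.3, headed "Measures to Minimize Bias: Randomization and Blinding", says only that the topic does not apply.
- **Eligibility on the same score.** Protocol Section 5.1, item 4: "Minimum score of 2 on the SGUS score for parotid and submandibular glands".
- **Timing.** Table 3 of the protocol summary has one pre-dose ultrasound, in the Day 1 column, with the comment "Schedule ultrasound 2 weeks before Day 1 to ensure results availability". Section 4.1 instead places that scan on Day 1 before the first dose.
- **Baseline.** SAP Section 4.1.3: "Baseline is the last nonmissing measurement obtained before the first administration of INCB050465".

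**The concern.** Read together, the eligibility rule, the single scheduled pre-dose scan and the baseline definition imply that the read which admits a participant is also the read against which response is judged. Because that read must be available before dosing, it cannot be mixed in with the later scans. The Week 4 and Week 12 scans come afterwards, all from treated participants, and nothing readable stops the reader from knowing which visit a scan belongs to.

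One grade in one of four glands is the smallest step on the scale, and it is enough to make a responder. With no control arm and no reference rate, a reader who grades later scans slightly more kindly would raise the primary percentage with nothing to set it against. The stake is how that percentage can be interpreted. No hypothesis is tested, so type I error is not the issue.

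**Working it through.** **Inputs from the documents.** Four glands, each graded 0 to 4; response is a fall of at least 1 in the sum; entry at a sum of at least 2; n = 12. The one numerical design claim (Protocol Section 10.1) concerns adverse events and reproduces: 1 − 0.8^12 = 0.931, above 90%. It says nothing about SGUS, and the documents give no read-error or repeatability figure.

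**Assumptions.** No true change. Each gland read is one grade too high with probability q and one grade too low with probability q, for q = 5%, 10% or 15%, independently across glands and reads. These values are a range for illustration, not estimates.

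**Step 1: symmetric noise.** The change in the sum is made of 8 independent gland-read errors (4 at baseline, 4 at follow-up). By symmetry, P(fall ≥ 1) = [1 − P(no net change)] / 2, where

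P(no net change) = Σ_k 8! / (k! k! (8 − 2k)!) × q^(2k) × (1 − 2q)^(8 − 2k).

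For q = 5% the terms are 0.4305 + 0.0744 + 0.0017 + 0.00001 = 0.5066, so P(fall ≥ 1) = (1 − 0.5066) / 2 = 0.247. The same sum gives 0.3321 for q = 10% and 0.2601 for q = 15%.

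**Step 2: leniency at follow-up.** Move 2.5 percentage points per gland from the upward to the downward error, at follow-up only. At q = 5% the follow-up errors become 7.5% down and 2.5% up. This converts half of the upward errors at that level, so it is not a small shift there.

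| q each way | Fall ≥ 1, noise only | Expected of 12 | Fall ≥ 1, with leniency | Excess (points) | Fall ≥ 2, noise only |
|---|---|---|---|---|---|
| 5% | 24.7% | 3.0 | 32.2% | 7.5 | 4.3% |
| 10% | 33.4% | 4.0 | 39.4% | 6.0 | 10.8% |
| 15% | 37.0% | 4.4 | 42.0% | 5.0 | 16.1% |

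**Step 3: reuse of the qualifying read.** Simulation of 400,000 participants per case, grades bounded at 0 and 4, entry at a sum of at least 2, comparing the qualifying read with an independent re-read as baseline:

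- True grades 1 to 3: 24.8/33.4/36.9% against 24.7/33.5/36.9%, so no visible effect.
- True grades 0 to 2: reuse adds roughly 1 to 2 points.
- Most glands at grade 0, so that many sums lie near the cut, q = 5%: 27.3% against 20.4%, a gap of 6.9 points.

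**Step 4: what each remedy touches.** Masked random-order reading removes the step 2 excess, and a re-read baseline removes the step 3 effect. Neither alters the noise-only column. A 2-point threshold does, as the last column shows.

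**Step 5: would the change summary reveal leniency?** Under symmetric noise the mean change is about 0. Under the step 2 shift it is 4 × (−0.025 − 0.025) = −0.20 points, which has the same sign and form as a drug effect.

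**The case against.** The strongest reply has four parts.

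1. **Protections already exist.** Reading is central and off site. SAP Section 7.2 and Table 2.1.1.2 report change in SGUS, and Listing 2.6.1 gives individual scores. Symmetric noise averages to zero, so it can be told apart from a downward shift, within the precision of 12 participants. This stands. It would be wrong to infer that masking is the only protection, or that a positive proportion could never be told apart from noise. The change summary uses the same reads, however, so it does not remove expectation bias.
2. **A masking rule may exist out of sight.** Protocol Section 8.2.1 has a redaction straight after the score definition, and vendor procedures are not in the documents. Section 6.3 can be read as addressing treatment allocation only. Nothing states that the reader knows the visit. This stands too: the supportable statement is that the readable text specifies no masking, not that the reads are unmasked.
3. **The baseline premise is inferred.** Table 3 and Section 4.1 disagree on the date of the pre-dose scan. Section 8.1.2 also lets routine imaging within 28 days of Day 1 serve as baseline. A separately read Day 1 scan would become the baseline under SAP Section 4.1.3. This stands, and the passages must be reconciled; the absence of stated masking is unaffected.
4. **Efficacy is exploratory** (SAP Sections 3.2 and 7). True, so no decision rule is biased. The primary result is still a percentage that readers will interpret.

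**Conclusion.** The point holds as a cheap improvement, with moderate confidence. The readable protocol and SAP specify no masking of visit order, and the qualifying read appears to serve as the primary baseline.

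The part due to expectation is about 5 to 8 percentage points under the assumed leniency shift. Reuse of the qualifying read adds about 0 to 2 points, and more only if many scores sit near the entry cut, which the documents do not indicate.

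A reader might infer that the 25/33/37% false-response rates measure the harm from unmasked reading. They do not: they are symmetric noise passing a 1-point cut, and masking leaves them unchanged. A reader might also pool the two visits into response at either one, but no such responder is defined. All SGUS rates here rest on assumed error levels.

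**What to change.** - Keep the pre-dose central read for eligibility only.
- After the last Week 12 scan, have the central vendor grade all three stored scans per participant (3 × 12 = 36) in random order, masked to participant and visit. Use those grades, including the re-read baseline, for the primary endpoint.
- State this in Protocol Section 6.3 and as an SGUS exception in SAP Section 4.1.3. If a vendor document already masks visit order, cite it in both places.
- Reconcile Table 3 and Protocol Section 4.1 on the date of the pre-dose scan.
- Add a row to SAP Table 2.1.1.1 for a fall of 2 points or more. This is the item that deals with read noise.

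**Cost.** About 12 extra baseline reads if the Week 4 and Week 12 reads are held to the end, or about 36 repeat reads if they are not. No new scan or visit is needed. SGUS results arrive later, and a re-read baseline may differ from the eligibility read.
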